8.1. Primary Efficacy Estimands

The primary efficacy estimands will differ for the EMA and FDA submissions based on guidance received from the different regulatory authorities. The full estimand definitions are provided in Section 3.2.

EMA Submission:

The estimand for progression of myopia is the difference in the mean annual progression rate using data through Month 24.

The primary efficacy analysis will test the following hypothesis:

- H_0 : The mean annual progression rate through Month 24 is equal between Vehicle and SYD-101.
- H_1 : The mean annual progression rate through Month 24 is different between Vehicle and SYD-101.

FDA Submission:

The estimand for progression of myopia is the difference in the proportion of participants with confirmed myopia progression >0.75 D at or before Month 36.

The primary efficacy analysis will test the following hypothesis:

- H_0 : The proportion of participants with myopic progression at or before Month 36 is equal between Vehicle and SYD-101.
- H_1 : The proportion of participants with myopic progression at or before Month 36 is different between Vehicle and SYD-101.

For submission to both the EMA and FDA, the primary efficacy analysis (EMA and FDA) will be tested at alpha=0.05 (2-sided) level of significance. Type 1 error for this study will be controlled using a Hochberg-based multiple-sequence gatekeeping procedure which will be implemented separately for EMA and FDA. The combination gatekeeping and a truncated Hochberg approach is accepted methodology for type I error control when there are multiple dose comparisons across multiple endpoints (Dmitrienko 2011).

Note there is no correction for multiplicity for the efficacy analysis between regulatory agencies as efficacy will be assessed independently by each regulatory agency, EMA or FDA, in their

respective submission. This is in accordance with ICH Guidance E17-General Principles for Planning and Design of MRCT where it is stated “because regulatory approvals are based on different primary endpoints by different authorities, no multiplicity adjustment is needed for regulatory decision-making.”

Each dose of SYD-101, 0.01% and 0.03%, will be independently compared to Vehicle. A truncated Hochberg adjustment with truncation parameter $\gamma = 0.80$ for FDA submission and $\gamma = 0.80$ for EMA submission will be performed to establish significance for comparisons of each of the active doses to Vehicle whilst controlling the overall type I error. For the primary efficacy endpoint, using the truncated Hochberg approach with a truncation parameter $\gamma = 0.80$, statistical significance at the 0.05 level will be achieved for both dose comparisons if both comparisons have p-values < 0.045 $[(\alpha \times (1+\gamma)/2)]$. If one dose comparison has a p-value ≥ 0.045 , then the other dose comparison p-value must be less than 0.025 $[\alpha/2]$ to be significant.

8.1.1. Primary Analysis

Calculation of SE:

The primary efficacy endpoints for EMA and FDA are based SE. SE values will be calculated for each autorefraction for each eye as the sum of the sphere power with half of the cylinder power (SE = sphere + $\frac{1}{2}$ cylinder). The SE for each measurement will be calculated for each eye and then averaged by eye; the participant's averaged right eye SE and averaged left eye SE will then be averaged (i.e., a single averaged SE value for a given visit will be obtained for each participant by taking the “average of the averages”).

Per protocol, the autorefraction procedure is to be performed 3 times in each eye. If there are less than three measurements for a given eye, the available SE values will be averaged for that eye prior to averaging the right and left per eye SE averages for the final average SE (over both eyes) value for analysis. This final per participant average of SE from the right and left eyes will be used for analysis.

The final average SE (over both eyes) will be considered missing if a non-missing SE measurement is not available for both eyes at a given visit. For a given eye, SE is considered non-missing if there is at least one measurement with a non-missing sphere and a non-missing cylinder value recorded for the same autorefraction measurement. If the baseline final average SE (over both eyes) is missing from the autorefraction, the SE assessment result from the manual refraction will be used.

Data imputations:

A combination of hypothetical, composite, and treatment policy strategies for intercurrent events will be used for the primary estimands as detailed in Section 3.2. For the EMA and FDA, intermittent missing data or observations post study or treatment discontinuation not due to a related AE, will be multiply imputed using via Markov Chain Monte Carlo (MCMC) methods assuming the missing data is MAR (Missing at Random). However, for by eye analysis data will be analyzed as observed.

For the EMA, observations after specified prohibited or escape treatment will be observed until day of prohibited or escape treatment; observations following prohibited or escape treatment will be censored and not imputed. For the FDA primary estimand, observations post prohibited or escape treatment will be considered non-responders.

For the EMA primary estimand, observations post study or treatment discontinuation due to a related AE will be multiply imputed assuming missing data is MNAR (Missing Not at Random). For the FDA primary estimand, observations post study or treatment discontinuation due to a related AE will be considered non-responders.

For the EMA and FDA, observations with invalid SE values will be analyzed as observed.

For any imputations, the value to be imputed is the average SE value (average of both eyes). This same set of imputed SE values will be used to calculate the primary efficacy endpoints for EMA and FDA, as well as the key secondary and applicable secondary efficacy endpoints derived from SE. All imputations will be based on set SEEDS. It is planned to perform k=50 imputations, however the number of imputations may be increased depending on the amount of missing data.

MAR imputations will be performed separately for each treatment arm and the imputation model will include terms for age at baseline, baseline SE (average of both eyes), and SE values (average of both eyes) for each post baseline scheduled visit through the specified analysis timepoint, Month 24 or Month 36 as applicable.

Imputations for data assumed to be MNAR will be first imputed via MCMC multichain methods to obtain monotone data as above for MAR imputations. The remaining missing SE values will be imputed via a sequential vehicle-based pattern imputation using regression methods ([Ratitch, 2011](#)) for the scheduled SE visits through the analysis timepoint, Month 24 or Month 36, using a model including age at baseline and baseline SE (average of both eyes) followed by sequential visits through M24 or M36, imputed values for those on SYD-101 treatment will be based on the Vehicle group.

Data sets will be sorted by treatment and participant id prior to imputation.

Valid SE Values:

Due to technical issues or non-compliant participants (e.g., wiggly child), not all SE assessments performed may be valid. For PPS sensitivity analysis based on valid SE values, the final average SE (over both eyes) will be calculated only if there is a valid per eye average SE for each eye. A per eye average SE value will be considered valid if there are three non-missing assessments performed for that eye. However, if there are three non-missing SE assessments for a given eye, but one of the SE values differs from the other two SE values for that eye by at least 1 D, only the two SE values that are within 1 D of each other will be considered valid and used to calculate the valid average SE for that eye. Otherwise, all three SE values will be used to calculate the per eye average SE. If there are only two non-missing assessments available for a given eye and the two SE values for that eye are within 0.45 D of each other (i.e., $-0.45 \text{ D} \leq \text{SE Measurement 1} - \text{SE Measurement 2} \leq 0.45 \text{ D}$) then the per eye average SE of those two assessments will be

considered valid. Otherwise, the per eye SE value will be considered invalid for that eye at that visit.

EMA Submission Analysis: Annual Progression Rate

The primary estimand of the primary objective is annual progression rate of myopia. The annual progression rate of myopia for a given timepoint will be calculated as the negative change in SE (average of both eyes) from baseline, divided by the number of days to the timepoint (visit date – date of first dose of study drug + 1), and multiplied by 365.25 days/year. The progression rate will be missing if the SE (average of both eyes) is missing. The multiply imputed average SE (over both eyes) will be used to derive the annual progression rate.

SYD-101 0.01% and SYD-101 0.03% will be compared to Vehicle for the annual progression rate of myopia after 24 months of treatment using a REML-based MMRM model including fixed effects for treatment group, baseline age category, categorical visit, and the treatment group by visit interaction, with baseline SE value as a covariate. No explicit structure will be assumed for the covariance among the repeated measures. However, in case there is a convergence problem with the unstructured covariance, then a compound symmetry covariance structure will be assumed. The Kenward-Roger Method will be used to calculate the denominator degrees of freedom for the test of fixed effects. All visits for the Month 24 analysis will be included in the model, with the primary comparison at the Month 24 visit.

The above model will be performed for each imputation and the results combined via SAS PROC MIANALYZE for final treatment estimates. The estimated mean annual progression rate of myopia for each treatment at each visit and the estimated mean difference between each SYD-101 treatment group and Vehicle at Month 24 will be presented along with their corresponding 95% CIs.

The analysis described above will be performed for annual progression rate of myopia by eye at Month 24 and repeated for the annual progression rate of myopia at Month 36 with the MMRM model including data for visits through Month 36 as a secondary analysis.

FDA Submission: Confirmed Progression > 0.75 D

Progression is defined as an increased negative change where change is calculated as visit value – baseline value. Progression will be considered missing if a valid SE measurement is not available for both eyes at the given visit. The multiply imputed SE data will be used to determine confirmed progression. For analyses, progression will be considered confirmed if at the next consecutive visit, regardless of the number of days from the prior visit, progression >0.75 D continues to be demonstrated.

The proportion of participants with confirmed myopia progression (>0.75 D) at Month 36 will be compared between each dose of SYD-101 and Vehicle using pairwise CMH tests to account for randomization factors (ie, baseline SE and age categories). The pairwise CMH tests will be performed and the Mantel-Haenszel common risk difference 95% CIs will be calculated for each of the k imputed datasets and the results combined via SAS PROC MIANALYZE for final treatment estimates. Point estimates and CIs will be presented in summary tables as percentages (i.e., the estimated proportions * 100).

Rubin's pooling methodology utilized in SAS PROC MIANALYZE is based on assumption that the estimates are asymptotically normally distributed. The CMH test follows a Chi-Square distribution which is highly skewed for smaller degrees of freedom and can violate Rubin's assumptions. Prior to combination of data in the MIANALYZE procedure, the individual CMH test statistics will be transformed to an approximate Normal (0,1) variables using the Wilson-Hilferty transformation ([Wilson & Hilferty, 1931](#); [Goria, 1992](#)).

The number and percentage of participants in each treatment group who meet the definition of myopic progression will be presented. These values will be based on the averages from the k imputations.

The same analysis will also be performed at Month 24 looking at progression at or before Month 24 as a secondary analysis.

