| | 
• Mean annual progression rate of myopia based on 36 months of follow-up for the US (24 months for EU) | The annual rate of myopic progression frequently appears in the literature as a key endpoint and therefore will serve as a reference to other clinical trials. Medical Products Agency (Sweden) requested a continuous variable as it provides for more information. |

| OBJECTIVE | ENDPOINT | JUSTIFICATION FOR ENDPOINT |
|---|---|---|
| Efficacy (continued) | | |
| To evaluate the efficacy of SYD-101 for slowing the progression of myopia in children | • Proportion of participants with annual myopia progression rate ≤ 0.50 D/year | A rate of progression of ≤ 0.50 D/year is considered very low and will add further characterization to the effects of SYD-101. |
| | • Proportion of participants with annual myopia progression rate ≤ 0.25 D/year | A change of ≤ 0.25 D is within testing error of autorefraction and is therefore considered to be negligible. |
| | • Proportion of participants with an increase of myopia of >0.50 D at Month 36 (Month 24 for EU) | Results of the ATOM2 study showed that 0.01% atropine reduced myopic progression by 0.49 D over 2 years (<0.25 D/year). As an endpoint, the proportion of patients with an increase of myopia of >0.50 D at Month 36 (Month 24 for EU) would enable comparison of this study's results with those of other clinical trials in addition to further characterizing the effects of SYD-101. |
| | • Time to progression of myopia >0.75 D | This measures the time to failure. |
| | • Mean annual progression rate on Subgroup of participants with refractive history of progression ≥ 0.5 D (month 24 for EU) | Patients with previous myopia progression are more likely to have worse subsequent progression. |
| | • Mean annual progression rate on Subgroup of participants with refractive history of progression ≥ 0.75 D (month 24 for EU) | Patients with previous myopia progression are more likely to have worse subsequent progression. |
| | • Mean change from baseline in axial length (at sites with the requisite equipment; at least 50% of study participants) | While myopia is primarily due to elongation of axial length, most pediatric clinics lack the biometry equipment to measure this. Therefore, axial length will be measured for participants enrolled at sites with the requisite equipment. |
| Exploratory | | |

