7.2 PARTICIPANT DISCONTINUATION/WITHDRAWAL FROM THE STUDY

Participants are free to discontinue the study at any time, for any reason, and without prejudice to further treatment. The investigator may remove a participant if, in the investigator's judgment, continued participation would pose unacceptable risk to the participant or to the integrity of the study data. Reasons for removal or withdrawal might include the following:

- Withdrawal of consent
- Administrative decision by the investigator or sponsor
- Significant protocol deviation
- Participant noncompliance or other significant protocol deviation
- Pregnancy
- Safety concern by the investigator or sponsor
- Lost to follow-up

With the exception of withdrawal of consent, participant withdrawal should be discussed with the sponsor, when possible, prior to withdrawing. Notification of early participant discontinuation from the study and the reason for discontinuation will be made to Syndexis and will be clearly documented on the appropriate eCRF. If a participant discontinues prior to completing the study, the procedures outlined for the Month 48 visit should be performed at the ET visit (ie, last visit the participant attends).

Participants who sign the ICF and are randomized but do not receive study drug may be replaced by randomization of an additional participant (ie, the replacement participant will not necessarily receive the same treatment assignment as the original participant being replaced). Participants who sign the ICF, are randomized and receive the study intervention, and subsequently withdraw, or are withdrawn or discontinued from the study, will not be replaced.

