Intercurrent event approaches for the three secondary efficacy endpoints which will not use the methods summarized in the above table are detailed below.

Data after receipt of prohibited treatment or escape therapy will be censored for the axial length and for the time to event estimands and multiple imputation will not be performed for these endpoints. The censoring and analysis methods utilize a hypothetical MAR approach for study discontinuation (regardless of reason), receipt of prohibited treatments or escape therapy.

Time to progression of myopia will be calculated in days as the date of first confirmed SE measurement that represents a reduction of >0.75 D or greater minus the date of first dose of study drug, plus one. Participants who do not experience myopic progression through 24 months (EMA) or 36 months (FDA) or who have an early discontinuation without a progression will be censored at the date of their last SE assessment at or before Month 24 (EMA) or Month 36 (FDA). Participants who receive a prohibited treatment or escape medication prior to myopic progression will be censored as of the date they received the prohibited treatment or escape medication.

For the analysis of annual progression rate for the fast progression subset, data after receipt of prohibited treatment or escape medication will be censored and multiple imputation will not be performed for this endpoint. The censoring and MMRM analysis methods will be utilized for study discontinuation (regardless of reason) and receipt of prohibited treatment or escape medication.

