Month 15	455	410 to 500
Month 18	546	501 to 591
Month 21	637	592 to 682
Month 24	728	683 to 773
Month 27	819	774 to 864
Month 30	910	865 to 955
Month 33	1001	956 to 1046
Month 36	1092	1047 to 1137
Month 39	1183	1138 to 1228
Month 42	1274	1229 to 1319
Month 48	1456	1320 to 1516

Visit Windows for Primary Analysis Endpoints

Scheduled Visit	Target Day	Analysis Visit Window (Days)
Screening	-21 to 1	Not applicable
Day 1	1	Not applicable
Month 6	182	2 to 273
Month 12	364	274 to 455
Month 18	546	456 to 637
Month 24	728	638 to 773 *Upper Limit M24 Cut Off
Month 30	910	774 to 1001
Month 36	1092	1002 to 1137 *Upper Limit M36 Cut Off
Month 42	1274	1138 to 1365
Month 48	1456	1365 to 1516

Only those assessments which are assigned to an analysis visit will be included in the summary tables and figures which are presented by visit. In the event, that there are multiple visits which fall into the same analysis visit window with non-missing data for an assessment and the visits include a scheduled and unscheduled visit(s), the assessment from the scheduled visit will be selected for analysis with one exception for BCVA. For BCVA, if there is a scheduled visit BCVA assessment and an unscheduled visit BCVA assessment in window performed on the same date, then the unscheduled visit BCVA assessment for that date will be used for analysis as it would be a re-test performed after refraction. If there are only unscheduled visit assessments performed within a window the visit closest to the target day of the study visit will be used for analysis. If there are two equal closest unscheduled visits occurring within the analysis visit

window (one before and one after the target day), then the earlier assessment will be used for analysis.

For summaries of an event at or before a given time point, such as progression at or before Month 24, all assessments (including unscheduled visits) on or before the Month 24 Visit or the upper limit of the corresponding visit window if no visit occurs in the Month 24 window, will be considered. All assessments will be presented in the data listings.

[figure not shown]

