4.3.5. Special Subsets

The SYD-101 Efficacy Subset will include all participants in the FAS who were randomized to one of the two active treatment arms and stay on active treatment for the entire 48-month study.

The Vehicle to Escape Efficacy Subset will include all participants in the FAS who were randomized to one of the two active treatment arms, were re-randomized to vehicle at Month 36, and initiated escape medication before Month 48.

For the EMA Submission, additional special subsets are defined based on refractive histories of participants prior to enrollment. Refractive history was required for participants presenting with myopia (SE) of < 0.75 D and requested of all other participants, if available. The refractive history will be used to calculate annual progression rate for three intervals.

- First Refraction History Date (RH1) to Screening
- Second Refraction History Date (RH2) to Screening (if two historical refractions are available)
- RH1 to RH2 (if two historical refractions are available, the earlier history will be considered RH1)

For each interval, the annual progression rate will be calculated as the change in SE divided by the number of days (later date – earlier date + 1) and multiplied by 365.25 to obtain an annual progression rate for that interval. Using the annual progression rates calculated for the intervals above, the following 2 subsets below are defined and the study annual progression rate will be analyzed for these subgroups as secondary endpoints for EMA only.

- Fast Progressor Subgroup 1: This subgroup will include all randomized participants in the FAS. With refractive history of ≥ 0.50 D progression/year for any of the three history time intervals. Intervals of less than 28 days will not be included as they can overestimate a progression rate. It is expected to have approximately 250 randomized participants meeting this criterion.
- Fast Progressor Subgroup 2: This subgroup will include all randomized participants in the FAS with refractive history of ≥ 0.75 D progression/year for any of the three history time intervals. Intervals of less than 28 days will not be included as they can overestimate a progression rate. It is expected to have approximately 200 randomized participants meeting this criterion.

5. Participant Disposition

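### The primary-endpoint Month 6 window opens on day 2 with no minimum interval for the annual rate, so an early-termination refraction can enter as a Month 6 rate of several D/year (minor; a loss of precision, not a bias, where no imputation is done)

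*SAP*

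**What the plan says.** SAP 8.1.1 defines the annual rate as the negative change in SE from baseline, "divided by the number of days to the timepoint", with days counted as "visit date – date of first dose of study drug + 1", then "multiplied by 365.25 days/year". It sets no minimum interval.

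SAP Section 4 has two window tables. The general Table 4-1 gives Month 6 as days 137 to 231. The separate table for the primary endpoints gives Month 6 as days 2 to 273. If a window holds both a scheduled and an unscheduled visit, "the assessment from the scheduled visit will be selected for analysis"; nothing removes a reading for being too early.

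The first scheduled post-baseline autorefraction is at Month 6. For a child who leaves before then, Protocol 7.2 says that "the procedures outlined for the Month 48 visit should be performed at the ET visit", and the schedule of activities includes cycloplegic autorefraction in that column.

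All visits enter the mixed model (MMRM), and the comparison is made at Month 24. The covariance is unstructured, with compound symmetry as the fallback. Estimated mean rates are to be presented for each arm at each visit. Sensitivity Analysis 7 uses no imputation. For the two EMA fast-progressor endpoints, SAP 3.3 says that "data after receipt of prohibited treatment or escape medication will be censored and multiple imputation will not be performed for this endpoint".

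**The concern.** Dividing by the actual day count multiplies the error in a single change by 365.25 over the number of days. At the Month 6 target day that factor is about 2; at week 3 it is about 17. A child who leaves in week 3 has no later reading to displace the early one, so the plan as written puts that value into the model as a Month 6 rate.

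Five places are exposed:
- Sensitivity Analysis 7
- the two fast-progressor endpoints
- the Month 6 estimates reported by arm
- the compound symmetry fallback, which pools the variance over visits
- the imputation model, which takes a near-baseline SE as a Month 6 SE

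An outlier of this kind would be noticed only once the data are analysed, so the rule should be settled beforehand.

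**Working it through.** **Plan's own figure.** For 280 per arm, a difference of 0.18 D/year, SD 0.60 and two-sided alpha 0.025, power is 0.905 by the normal approximation and 0.903 by the noncentral t. This agrees with the stated >90%. It does not depend on the windows; it gives the scale for what follows.

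**Rate produced by error alone.** Protocol Section 3 says: "A change of ≤ 0.25 D is within testing error of autorefraction". Rate = 0.25 × 365.25 / day:
- day 14: 6.52 D/year
- day 21: 4.35
- day 28: 3.26
- day 92: 0.99
- day 137: 0.67
- day 182: 0.50

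The means assumed in the SAP 4.1 simulations are 0.65 and 0.325 D/year.

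**How many children.** SAP 4.1 assumes 7% loss per year. Leavers by day 136 per arm: 280 × (1 − exp(−0.07 × 136/365.25)) = 7.2. For a fast-progressor sample of about 250 (SAP 4.3.5), split 83 Vehicle to 167 pooled active, the same fraction (7.2/280 = 0.0257) gives about 2 and 4.

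**Analyses without imputation, unstructured covariance.** Simulation assumptions: rates 0.65 and 0.325, SD 0.55, 7% loss per year, SE measurement SD 0.15 D (not in the documents). Two runs (800 and 1,500 replicates) had every leaver refracted at ET. The increase in the SD of the Month 24 difference, against dropping SE before day 137, was:
- ET refractions from day 2: +42% to +50%; second run +40% to +43%
- from day 7: +11% to +13%; second run +9% to +11%
- from day 14: +5%; second run +4% to +5%
- from day 28: 0% to +2%; second run +1%

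With half of leavers refracted, from day 14, it was +1% to +2%. In the second run the mean difference stayed at about −0.325 in every scenario. The steep fall with the starting day is expected, because the error variance of a rate varies as 1/day².

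**Compound symmetry fallback and Month 6 spread.** A separate check used 217 per arm, with early readings on days 14 to 42. The standard error of the Month 24 difference rose from 0.061 to 0.063 with 2 early readings per arm and to 0.070 with 10 (error SD 0.15 D), or from 0.069 to 0.075 and 0.088 (error SD 0.25 D). The SD of the Month 6 rate rose from 0.72 to 0.79 and 0.99, or from 0.91 to 1.10 and 1.45. This check kept the children's later visits, so it shows the effect on the pooled variance and not the full behaviour of leavers.

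**Imputed EMA primary.** A day-21 SE taken as Month 6 omits 161 days of progression. On Vehicle that is 0.65 × 161/365.25 = 0.29 D; on SYD-101 it is 0.325 × 161/365.25 = 0.14 D. If the shortfall carries through to Month 24 (728/365.25 = 1.99 years), the child's rate is too low by 0.14 or 0.07 D/year. Averaged over an arm: 0.14 × 7.2/280 = 0.0036 and 0.07 × 7.2/280 = 0.0018 D/year, both under 0.005.

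**The case against.** The strongest reply is that the consequence is small, and most of that stands.

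- A reader might infer that the primary result is at risk. The documents do not support this. The comparison is at Month 24, data after discontinuation are imputed, and the shift is under 0.005 D/year on an arm mean against a planning difference of 0.18. It is larger on Vehicle, so it slightly shrinks the treatment effect. The FDA primary uses confirmed progression, not an annualised rate.
- A reader might infer from the historical-refraction rule in SAP 4.3.5, "Intervals of less than 28 days will not be included as they can overestimate a progression rate", that the SAP concedes the same bias on study. It does not. That rule protects a one-sided classification, in which any of three intervals above a cut-off qualifies a child, and there noise does push upward. The on-study rate is a signed mean, so noise cancels on average.
- A reader might take increases of 40% or more as typical. They require every leaver to be refracted and some refractions to fall in the first week. The documents give no such rate, and Protocol 7.3 implies that some leavers have no ET visit at all.
- The fast-progressor endpoints are tested only after the primary and five earlier secondary endpoints have succeeded.

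Two points limit the reply. Sensitivity Analyses 2 to 7 use data after treatment discontinuation as observed, so an ET refraction made off drug still counts there. The SAP also does not say how a refraction on the day of discontinuation is classed in the primary analysis.

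**Conclusion.** The point holds as a minor defect in a window boundary. Followed literally, the plan labels a reading taken weeks after baseline as a Month 6 rate of several D/year.

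In the analyses without imputation this costs precision and introduces no bias. The SD of the Month 24 difference rises by about 0-5% when ET refractions start at day 14 or later, and by about 11-13% (9-11% in the second run) when they start at day 7. The Month 6 estimates by arm and the compound symmetry fallback become noisier, and the imputation model receives a mislabelled SE. The imputed EMA primary is essentially unchanged.

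These sizes rest on the SAP's 7% annual loss and on an assumed SE measurement SD of 0.15 D. The number and timing of early ET refractions are not given.

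**What to change.** Start the Month 6 window for the primary endpoints at day 137, the lower limit already in the general Table 4-1. Add one sentence: SE taken on days 2 to 136 is listed and still counts towards progression events up to a time point, but is not annualised, entered in the MMRM or used as Month 6 SE in the imputation. Day 137 limits the rate from a 0.25 D error to 0.67 D/year. A floor near day 92 would also serve (0.99); a 28-day floor would not (3.26).

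The cost is one table entry and one sentence, plus a small downside that the SAP should state. About 7 or fewer children per arm with no later SE would be fully imputed in the primary analysis and would contribute no record to the MMRM analyses without imputation. The SAP should also say whether a listed early SE still meets the per-protocol set's requirement for one post-baseline SE.
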